6.2 Definition Relapsed Myeloma and Refractory Myeloma

An ASH/FDA panel has recommended to include clinical criteria to define relapsed myeloma and to separately analyze data for the relapsed as opposed to the refractory group of patients⁵². In accordance with this consensus statement, International Myeloma Working Group diagnostic criteria⁵⁰, and the international uniform response criteria⁵¹ the following definitions will be used:

6.2.1 Refractory Myeloma

Biochemical or clinical evidence of loss of disease control within 60 days after the last therapy. Any of the following defines refractory myeloma:

1. Progressive disease (see 8.1.1) on prior therapy
2. Best response to prior therapy was stable disease (see 8.1)
3. Progressive disease (see 8.1.1) within 60 days of the last therapy

6.2.2 Relapsed Myeloma

Not fulfilling criteria for refractory disease and at least one biochemical *and* at least one clinical criterion fulfilled indicating recurrence of disease more than 60 days after the last therapy:

One or more biochemical criteria for recurrent disease:

An increase of 25% from lowest response value in any one or more of the following, verified on two consecutive measurements:

1. Serum M-component (absolute increase must be ≥ 0.5 g/100 ml) *
2. Urine M-component (absolute increase must be ≥ 200 mg per 24 h)
3. Only in patients without measurable serum and urine M-protein levels: the difference between involved and uninvolved FLC levels (absolute increase must be >100 mg/l)
4. Bone marrow plasma cell percentage (absolute % must be $\geq 10\%$)

AND one or more clinical criteria for recurrent disease:

Any of the following:

1. Definite development of new bone lesions or soft tissue plasmacytomas

2. Definite increase in the size of existing bone lesions or soft tissue plasmacytomas. A definite increase is defined as a 50% (and at least 1 cm) increase as measured serially by the sum of the products of the cross-diameters of each measurable lesion
3. Development of hypercalcemia (corrected serum calcium >11.5mg / 100ml) that can be attributed solely to the plasma cell proliferative disorder
4. Decrease of hemoglobin by at least 2g/dL below the best independent value (without ESA or blood transfusion for at least 28 days) since the end of previous therapy or new decrease in HgB below 10g/dL or to 2g/dL below the lower limit of normal
5. New increase in serum creatinine to > 2mg/dL, or increase by 2mg/dL attributed to myeloma progression

*: If the starting serum m-protein level is ≥ 5 g/dL an absolute increase of ≥ 1 g/dL, verified on two consecutive measurements, is sufficient as a biochemical criterion for recurrent disease.

7 Treatments

7.1 Investigational therapy

7.1.1 Panobinostat

Panobinostat (also known as LBH589) will be provided by Novartis. Oral panobinostat will be supplied as 5-mg, 15-mg, or 20-mg pink/opaque-colored, hard gelatin capsules.

Medication labels will comply with US legal requirements and be printed in English. They will supply no information about the patient. The storage conditions for study drug will be described on the medication label.

During the study, panobinostat will be administered orally as once daily dose of 20 mg. according to the schedule in 5.3.

Patients should be instructed to take their once-a-day oral dose of panobinostat at the same time each morning. Each dose of panobinostat should be taken with an 8 oz / 240 ml glass of water after a meal. Patients should be instructed to swallow the capsules whole and not chew them. Patients must avoid grapefruit or grapefruit juice and seville (sour) oranges during the entire study.

On the days of ECG monitoring, drug administration should be supervised by study center personnel and administration time should be recorded. Subsequently, ECGs should be performed at the predefined time points.)

If the patient forgets to take his/her dose during the morning on scheduled treatment day, then he/she should take panobinostat (LBH589) on that same day within 12 hours after the missed dose if possible. After more than 12 hours, that day's dose should be withheld, and the patient should wait to take LBH589 until the next scheduled treatment day (i.e., patients should be instructed not to try to make-up the missed dose after 12 hours). The patient should then continue treatment with the original dosing schedule

The investigator should instruct the patient to take the study drug exactly as prescribed (promote compliance). All dosages prescribed and dispensed to the patient and all dose changes during the study should be recorded.

7.1.2 MLN9708 (Ixazomib)

All protocol-specific criteria for administration of study drug must be met and documented before drug administration. Study drug will be administered only to eligible patients under the supervision of the investigator or identified sub investigator(s). Patients should be monitored for toxicity, as necessary, and doses of MLN9708 should be modified as needed to accommodate patient tolerance to treatment; this may include symptomatic treatment, dose interruptions, and adjustments of MLN9708 dose (see under 7.5).

7.1.2.1 MLN9708 (Ixazomib) Administration

Capsules of MLN9708 will be supplied by Millennium as capsules of 2.3 mg, 3.0 mg, and 4.0 mg MLN9708.

The prescribed administration of MLN9708 doses and schedules in this study are outlined in 5.3

Patients should be instructed to swallow MLN9708 capsules whole, with water, and not to break, chew, or open the capsules. Study drug should be taken on an empty stomach (no food or drink) at least 1 hour before or 2 hours after a meal. A total of approximately 8 ounces (240 mL) of water should be taken with each capsule.

Missed doses can be taken as soon as the patient remembers if the next scheduled dose is 72 hours or more away. A double dose should not be taken to make up for a missed dose. If the patient vomits after taking a dose, the patient should not repeat the dose but should resume dosing at the time of the next scheduled dose.

7.1.2.2 MLN9708 Destruction

Investigational MLN9708 (expired or end of study) should be destroyed on site according to the institution's standard operating procedure. Be sure to document removal and destruction on drug accountability logs.

7.1.2.3 Packaging, and Labeling of MLN9708

For blistered material, the capsules are packaged in cold form foil-foil blisters with a paper backing for child-resistance.

MLN9708 is an anticancer drug and as with other potentially toxic compounds caution should be exercised when handling MLN9708 capsules.

The study drug MLN9708 capsules will be provided by Millennium. The study drug will be labeled and handled as open-label material, and packaging labels will fulfill all requirements

specified by governing regulations. The formulation consists of 0.5-, and 2.0-mg capsules for oral administration.

MLN9708 capsules should be stored unopened at 2°C to 8°C (36°F-46°F). The capsules are individually packaged in cold form foil-foil blisters in a child-resistant package. The 0.2-, 0.5-, and 2.0 mg capsules are in 1 × 4 blister strips that are individually perforated. The strips (1 × 4) are placed in cartons containing 6 strips (24 total capsules) of the same strength. The 2.3-, 3.0-, and 4.0 mg capsules are supplied as a 1 x 3 blister card in a child-resistant cardboard wallet.

Storage, Handling, and Accountability

Upon receipt at the investigative site, MLN9708 should remain in the blister and carton provided until use or until drug is dispensed. The container should be stored at the investigative site refrigerated (36°F to 46°F, 2°C to 8°C). All excursions should be brought to Millennium's attention for assessment and authorization for continued use. Ensure that the drug is used before the retest expiry date provided by Millennium. Expiry extensions will be communicated accordingly with updated documentation to support the extended shelf life.

In countries where local regulations permit, MLN9708 capsules dispensed to the patient for take-home dosing should remain in the blister packaging and refrigerated as noted above until the point of use. The investigative site is responsible for providing the medication to the patient in the correct daily dose configurations. Approval for any patient for take-home medication must be discussed with Millennium in order to ensure the greatest conformity with repackaging, labeling, and patient compliance. Comprehensive instructions should be provided to the patient in order to ensure compliance with dosing procedures. Patients who are receiving take-home medication should be given only 1 cycle of medication at a time. Patients should be instructed to store the medication refrigerated (36°F to 46°F, 2°C to 8°C) for the duration of each cycle. Patients should be instructed to return their empty blister packs to the investigative site, rather than discarding them. Reconciliation will occur accordingly when the patient returns for their next cycle of take-home medication. Any extreme in temperature should be reported as an excursion and should be dealt with on a case-by-case basis.

Because MLN9708 is an investigational agent, it should be handled with due care. Patients should be instructed not to chew, break, or open capsules. In case of contact with broken capsules, raising dust should be avoided during the clean-up operation. The product may be harmful by inhalation, ingestion, or skin absorption. Gloves and protective clothing should be worn during clean-up and return of broken capsules and powder to minimize skin contact.

The area should be ventilated and the site washed with soap and water after material pick-up is complete. The material should be disposed of as hazardous medical waste in compliance with federal, state, and local regulations.

In case of contact with the powder (e.g., from a broken capsule), skin should be washed immediately with soap and copious amounts of water for at least 15 minutes. In case of contact with the eyes, copious amounts of water should be used to flush the eyes for at least 15 minutes. Medical personnel should be notified. Patients are to be instructed on proper storage, accountability, and administration of MLN9708, including that MLN9708 is to be taken as intact capsules.

7.1.3 Cardiac precautions

All patients must have an assessment of serum potassium, magnesium, and calcium (total corrected for albumin, or ionized calcium) ≤ 72 hours prior to the administration of oral panobinostat on day 1 of cycle 1 and the results must all be \geq LLN before the first dose of panobinostat is administered. Throughout the study serum biochemistry values including serum potassium, calcium, and magnesium will be monitored closely. On any day and time in which serum potassium, calcium, and magnesium are assessed, if the value is $<$ LLN, then the patient's potassium, calcium, or magnesium should be immediately supplemented following the availability of that laboratory result, in order to minimize the time patients have low values. Patients must then undergo a repeat biochemistry test to demonstrate values \geq LLN. These values must be \geq LLN before the patient is re-dosed with oral panobinostat.

Patients must be instructed to not take panobinostat if their most recent biochemistry values demonstrates potassium, calcium, or magnesium $<$ LLN. At a minimum, potassium, magnesium, and calcium will be checked according to the protocol. More frequent testing should be done if clinically indicated, e.g. patient has had prior low values, patient is taking medications (e.g., diuretics) that can result in lowering of their potassium, magnesium, or calcium levels.

7.2 Dexamethasone

Dexamethasone will be prescribed as 4mg tablets and charged to the patient's insurance. Dexamethasone tablets should be taken after breakfast with approximately 8 ounces (240 mL) of water. Missed doses can be made up until 72h from the next planned dose. Adherence will be evaluated together with adherence to investigational therapy.

7.3 Mandatory concomitant therapy

7.3.1.1 Herpes prophylaxis

The risk for shingles is increased with proteasome inhibition and can be decreased with prophylactic acyclovir⁵³. All patients will receive prophylaxis with acyclovir 400mg orally twice a day or valacyclovir 1000mg orally once a day. If the creatinine clearance of a patient drops below 30ml/min while a patient is on study, acyclovir should be reduced to 200mg twice a day and valacyclovir to 500mg orally once a day.

7.4 Instructions for Initiation of a New Cycle

A new course of treatment may begin on the scheduled Day 1 of a new cycle (cycle 2 and beyond) if:

- $ANC \geq 1.0 \times 10^9/L$ (G-CSF and GM-CSF are allowed to achieve this threshold)
- Platelets $\geq 50 \times 10^9/L$, without platelet transfusion for $\geq 72h$
- AST and $ALT \leq 3 \times ULN$
- Serum bilirubin $\leq 3 \times ULN$
- Serum potassium $\geq LLN$ and serum magnesium $\geq LLN$ (electrolyte levels may be achieved with repletion or other supportive medications like potassium sparing diuretics)
- $QTcF \leq 480$ msec if ECG obtained (mandatory before cycle 2)
- Any non-hematologic drug-related adverse events that may have occurred have resolved to \leq grade 1 or baseline severity. Physician discretion may be used in initiating the next cycle of treatment if the only toxicities that have not resolved to \leq grade 2 severity are dexamethasone-related toxicities.

If these conditions are not met on Day 1 of a new cycle, the subject will be evaluated at least weekly and a new cycle of treatment will not be initiated until the toxicity has resolved as described above. If a prolonged QTcF prevents re-initiation of therapy for more than 7 days the patient will be taken off study. For phase I patients only: If other criteria to initiate a new cycle are not met by 14 days after the planned start of a new cycle patients also go off study.

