10. Other concurrent severe and/or uncontrolled medical conditions (e.g., uncontrolled diabetes or active or uncontrolled infection) including abnormal laboratory values, that could cause unacceptable safety risks or compromise compliance with the protocol
11. Patients using medications that have a relative risk of prolonging the QT interval or inducing torsade de pointes if treatment cannot be discontinued or switched to a different medication prior to starting study drug. If an alternative medication that does not risk QT prolongation can safely be used in the opinion of the treating physician and the treatment is changed to that medication, the patient may be enrolled.
12. Patients who have not passed the nadir of bone marrow suppression from previous anti-myeloma therapy yet. If in doubt, serial CBCs with differential should be obtained.
13. The corticosteroids prednisone and dexamethasone may be continued until the day before treatment start if all related adverse events are controlled at CTCAE version.4.03 grade \leq 1.
14. Patients who have received radiation therapy to more than half of the pelvis or more than half of the spine within \leq 2 weeks prior to starting study treatment; or who have not yet recovered from side effects of such therapies.
15. Patients who have undergone major surgery \leq 4 weeks prior to starting study drug or who have not recovered from side effects of such therapy
16. Systemic treatment, within 14 days before study enrollment, with strong inhibitors of CYP1A2 (fluvoxamine, enoxacin, ciprofloxacin), strong inhibitors of CYP3A (clarithromycin, telithromycin, itraconazole, voriconazole, ketoconazole, nefazodone, posaconazole) or strong CYP3A inducers (rifampin, rifapentine, rifabutin, carbamazepine, phenytoin, phenobarbital), or use of Ginkgo biloba or St. John's wort.
17. Ongoing or active systemic infection, known human immunodeficiency virus (HIV) positive, known active hepatitis B virus hepatitis, or known active hepatitis C virus hepatitis.
18. Concurrent diagnosis of another malignancy if either systemic treatment or surgery is expected to be required within 2 years from study entry.
19. Known allergy to any of the study medications, their analogues, or excipients in the various formulations of any agent.
20. Patients with any significant history of non-compliance to medical regimens or unwilling or unable to comply with the instructions given to him/her by the study staff.

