7.6.1 Study drug discontinuation

It will be documented whether or not each patient completed the clinical study. If for any patient either study treatment or observations were discontinued, the reason will be recorded in the source documents and within ONCORE.

Patients will be informed that they have the right to withdraw from the study at any time for any reason, without prejudice to their medical care. The investigator also has the right to withdraw patients from the study for any of the following reasons:

1. Disease progression, this always requires removal from study
2. Adverse event(s)
3. Abnormal laboratory value(s)
4. Abnormal test procedure result(s)
5. For phase I patients only: Dosing delay of > 21 days (= unable to receive study therapy for 22 days including any therapy held during a cycle)
6. For phase I patients only: Delay of a cycle by > 14 days from the intended day of the next scheduled dose, counted from the start of the previous cycle.

7. Protocol violation
8. Subject withdrew consent
9. Lost to follow-up
10. Administrative problems
11. New anti-myeloma therapy started
12. Study Termination
13. Death

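### The exception to the grade 1 restart rule in 7.4 is set at grade 2, so read literally a lone grade 2 dexamethasone toxicity above baseline blocks the next cycle while a lone grade 3 one permits a start at discretion

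*Combined protocol and SAP*

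**What the plan says.** All references are to the combined protocol and SAP.

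- **Rule (7.4, last bullet).** A new cycle may start if "Any non-hematologic drug-related adverse events that may have occurred have resolved to" the general threshold, which is at most "grade 1 or baseline severity".
- **Exception (next sentence).** "Physician discretion may be used in initiating the next cycle of treatment if the only toxicities that have not resolved to" a second threshold are all of one kind. That threshold carries a ≤ sign, and the sentence ends "grade 2 severity are dexamethasone-related toxicities".
- **If the conditions fail.** The patient is seen at least weekly and "a new cycle of treatment will not be initiated until the toxicity has resolved as described above". The footnote to Table 8-1 repeats that a cycle depends on the 7.4 criteria.
- **Long delays.** 7.4 has an off-study rule, "For phase I patients only: If other criteria to initiate a new cycle are not met by 14 days after the planned start", and 7.6.1 item 6 lists "For phase I patients only: Delay of a cycle by > 14 days from the intended day of the next scheduled dose". Both are confined to phase I. Section 7.6.2 also requires discontinuation for a dose delay of more than 14 days, and gives no phase limit.
- **Dexamethasone's own rules.** Table 7-3 gives it three reduced levels and then a stop. For other non-hematologic toxicities, Table 7-4 makes holding the responsible drug optional at grade 2 (where quality of life is affected). At grade 3 it directs a hold until grade 1 or baseline. Table 7-4 also applies on the intended dosing day.
- **Baseline (6.1.2, exclusion item 13).** "The corticosteroids prednisone and dexamethasone may be continued until the day before treatment start if all related adverse events are controlled at CTCAE" grade 1 or lower.

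**The concern.** An exception to a grade 1 rule should reach the cases that fail at grade 1. This one reaches only those that fail at grade 2. A dexamethasone toxicity at exactly grade 2 fails the rule and, on the words used, is also outside the exception.

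Section 7.4 controls Day 1 of every cycle from cycle 2 onwards, and phase II treatment has no six-cycle limit. A literal block withholds panobinostat and ixazomib as well as dexamethasone, for a toxicity of the one drug that has its own reduction ladder. That sits badly with 7.5.1, which allows dose adjustment so that patients can stay on treatment. An investigator who follows the words and one who follows the likely purpose would treat the same patient differently.

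**Working it through.** The plan gives no figure to reproduce. The check applies the two sentences of 7.4 grade by grade.

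**Step 1. Lone dexamethasone-related toxicity, above baseline, literal reading.**

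| Grade | Meets the grade 1 rule? | Still above grade 2, so within the exception? | Result |
|---|---|---|---|
| 1 or lower | yes | not needed | start |
| 2 | no | no | blocked |
| 3 or higher | no | yes | physician discretion |

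The milder state is blocked and the more severe one is open. This inversion needs no assumption about other drugs.

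**Step 2. Add toxicities of the other drugs.** Write (other, dex) for the worst other-drug grade and the worst dexamethasone-related grade, each classed as 1 (or lower), 2 or 3 (or higher), with baseline at grade 1 or lower. (1,1) may always start.

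- If the exception excuses dexamethasone-related toxicities only, the sole cell open to discretion is (1,3). The only milder blocked cell is (1,2), giving 1 inverted pair.
- If it also waives the grade 1 rule for the other drugs, (2,3) opens too. The inverted pairs are then (1,2)–(1,3), (1,2)–(2,3), (2,1)–(2,3) and (2,2)–(2,3), which makes 4.

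The text does not say which scope applies. One pair is certain; the other 3 are conditional.

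**Step 3. Does another section cure it?**

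- *Baseline.* A patient whose grade 2 finding was already present at baseline passes the rule. Patients who took prednisone or dexamethasone until the day before treatment had to have steroid-related events at grade 1 or lower, so for them a later grade 2 event is above baseline.
- *Table 7-3* gives dose levels but no restart threshold.
- *Table 7-4* is stricter at grade 3 than at grade 2, the opposite order to the literal 7.4.
- *7.5.1* allows clinical judgment about which drug to hold or modify in situations its tables do not cover. It does not waive 7.4.

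**Step 4. How far can a block go?** With weekly review, checks fall on days 7 and 14 after the planned start. A toxicity still at grade 2 on day 14 takes the delay past 14 days. The off-study rules in 7.4 and 7.6.1 then apply to phase I only, but 7.6.2 as worded applies to phase II patients too.

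**Step 5. Does a changed threshold remove the inversion?** With the exception set at grade 1 or baseline and confined to dexamethasone, the cells open to discretion are (1,2) and (1,3), leaving 0 inverted pairs. With an added grade 2 cap, only (1,2) is open, again leaving 0. The two versions differ in (1,3) alone.

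**The case against.** **The purpose is plain enough.** The sentence is a permissive carve-out. If a physician may start despite a grade 3 dexamethasone toxicity, a grade 2 one is covered all the more, and the other drugs stay under the grade 1 rule. This is plausible and probably close to what was meant. It supports treating the defect as a drafting slip. It does not make the sentence safe, because a grade 2 cap for dexamethasone would explain the same words and gives a different answer at grade 3.

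**The condition could count as met when nothing exceeds grade 2.** Grade 2 dexamethasone toxicity would then be open to discretion. On those words, however, so might grade 2 panobinostat or ixazomib toxicity. A reader might infer that the grade 1 rule is defeated for those two drugs. The text does not compel that, since it nowhere says that the exception excuses anything but dexamethasone-related toxicities. For the same reason, 4 inversions cannot be claimed as established.

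**The symbol before grade 2 might have been misread.** A strict less-than sign would remove the problem. Nothing in the documents suggests a misreading, so this remains speculation.

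**Dexamethasone itself would not be restarted at grade 3.** This stands. A reader might infer from 7.4 alone that the drug causing a grade 3 toxicity can be given again. Table 7-4 holds it, so discretion there concerns panobinostat and ixazomib.

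**No size of effect is shown.** This also stands. One could calculate that a one-week wait cuts dose per unit time to 28/35 = 80%, but that holds for any one-week delay from any cause, and the documents give no resolution time. Section 2 reports phase I grade 1/2 events only where they were possibly related to panobinostat or ixazomib, so the frequency of the blocked case cannot be estimated.

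**Conclusion.** The point holds as a minor error in an operative dosing rule. Its certain size is one inversion: a lone dexamethasone-related toxicity above baseline blocks all three drugs at grade 2 and opens discretion at grade 3. This rests on the literal reading of the threshold as printed. The likely intent was discretion for dexamethasone toxicities that miss the general threshold, but the documents do not settle whether a cap was also meant.

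The effect is on cycle starts, at unknown frequency. DLT is assessed in cycle 1, before 7.4 applies, so DLT and dose selection are unaffected, and so are the planned analyses. A reader of 7.4 and 7.6.1 alone might infer that a blocked phase II patient merely waits. Section 7.6.2 does not support that, because a block of more than 14 days could lead to removal. Removal is a possibility under a prolonged block and is not shown to be common.

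**What to change.** Replace the exception in 7.4 with wording such as: *The physician may choose to start the cycle when every non-hematologic drug-related toxicity still above both grade 1 and baseline is attributed to dexamethasone. Toxicities of the other study drugs must meet the grade 1 or baseline rule. At grade 3 or higher, dexamethasone itself stays held under Table 7-4.*

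If the sponsor meant a cap, add that this discretion applies only when the dexamethasone-related toxicity is at grade 2 or lower. The sponsor should state which was meant, because the two versions differ for a lone grade 3 dexamethasone toxicity. The same edit could say whether the 14-day limit in 7.6.2 is meant for phase II.

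The cost is a short text change, with no added visits, tests or patients.
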